2.3.3. Milrinone

Milrinone is a phosphodiesterase 3 (PDE3) inhibitor with inotropic and lusitropic effects that was approved in the 1980s for intravenous use in decompensated congestive heart failure.

Vascular PDE3 breaks down cAMP in arterial smooth muscle cells and myocardium. By inhibiting PDE3, milrinone also functions as a vasodilator independent of β 1-adrenergic receptor stimulation and has been called an “inodilator” because of these dual effects (figure 2 and 3) (Opie 1986, Lakshminrusimha and Steinhorn 2009, Lakshminrusimha and Steinhorn 2013). Milrinone increases cAMP levels in cardiac muscle and vascular cells, improving ventricular function both directly and by reducing afterload (Lakshminrusimha, Konduri et al. 2016). Intravenous or enteral sildenafil (a PDE5 inhibitor) is another pulmonary vasodilator with potential for use in CDH and is currently being investigated for chronic use in severe diaphragmatic hernia (NCT00133679). (Abman, Kinsella et al.)

Animal models of PPHN: In an ovine model of PPHN induced by antenatal ductal ligation, milrinone relaxed pulmonary arterial rings in a dose dependent manner (Lakshminrusimha, Porta et al. 2009). This model of PPHN is associated with significant remodeling of the pulmonary artery with smooth muscle hypertrophy and muscularization of small, distal pulmonary arteries (Wild, Nickerson et al. 1989) similar to that described in infants with PPHN and CDH and was used in preclinical studies for iNO (Zayek, Cleveland et al. 1993). In the same model, an intravenous loading dose of 100 μ g/kg followed by 1 μ g/kg/min for an hour reduced pulmonary vascular resistance from 0.503 ± 0.06 mmHg/mL/kg/min to 0.383 ± 0.03 mmHg/mL/kg/min ($p < 0.05$) and was not associated with a significant decrease in systemic mean blood pressure (54 ± 3 to 51 ± 4 mmHg) (Rashid, Morin et al. 2006). In lungs isolated from lambs with PPHN, protein levels of adenylate cyclase and PDE3A (the predominant PDE3 isoform in vascular tissue) were similar to control lambs without any change in PDE3A activity suggesting that the target enzymes for milrinone were unchanged by vascular remodeling in PPHN (Lakshminrusimha, Porta et al. 2009).

Milrinone improves left ventricular output following cardiac surgery: The benefits of milrinone in children following surgery for congenital heart disease have been well established in several studies (including the randomized, double-blind PRIMACORP study, $n=238$)(Chang, Atz et al. 1995, Bailey, Miller et al. 1999, Hoffman, Wernovsky et al. 2002, Hoffman, Wernovsky et al. 2003). The PRIMACOR study was a double-masked, placebo-controlled trial conducted in neonates and young children following cardiac surgery (Hoffman, Wernovsky et al. 2003). Three parallel groups (low dose, 25 μ g/kg bolus over 60 minutes followed by a 0.25 μ g/kg per min infusion for 35 hours; high dose, 75 μ g/kg bolus followed by a 0.75 μ g/kg per min infusion for 35 hours; or placebo) were studied. The composite end point of death or the development of low cardiac output syndrome (LCOS) was evaluated at 36 hours and up to 30 days after randomization. Among 238 treated patients, 25.9%, 17.5%, and 11.7% in the placebo, low-dose milrinone, and high-dose milrinone groups, respectively, developed LCOS in the first 36 hours after surgery. High-dose milrinone significantly reduced the risk the development of LCOS compared with placebo, with a relative risk reduction of 55% ($P = 0.023$) in 238 treated patients

and 64% ($P = 0.007$) in 227 patients without major protocol violations. There were 2 deaths, both after infusion of study drug. The use of high-dose milrinone reduced the risk of the LCOS through the final visit by 48% ($P = 0.049$). This study established that the role of high-dose milrinone after pediatric congenital heart surgery to reduce the risk of LCOS.

Case reports of milrinone use in PPHN not due to CDH: Anecdotal reports have shown that milrinone can be an effective therapeutic option in PPHN. (McNamara, Laique et al. 2006, Bassler, Kreutzer et al. 2010) These retrospective case reports from two different hospitals in Ontario, Canada looked at 24 critically ill late preterm/term infants (except one infant at 26 weeks postmenstrual age PMA) with HRF or PPHN unresponsive to iNO. Bassler et al reported 4 infants with PPHN. Some of the infants were “primed” with normal saline (15ml/kg) and administered a loading dose of 50 $\mu\text{g}/\text{kg}$ over 30 min followed by 0.33 $\mu\text{g}/\text{kg}/\text{min}$. None of the infants developed systemic hypotension, and all of them showed consistent improvement in oxygenation. One of the infants was born at 26 weeks PMA and developed bilateral intraventricular hemorrhage (IVH) with moderate dilation of all ventricles. Another term infant developed an IVH. The third infant (39 weeks PMA) showed a small left subependymal hemorrhage. In a subsequent study, McNamara et al reported 9 term infants with PPHN with poor response to iNO who received IV milrinone. Because of the potential risk of systemic hypotension, a loading dose was avoided in these patients with PPHN. The infusion was started at 0.33 $\mu\text{g}/\text{kg}/\text{min}$ and increased in increments of 0.33 according to clinical response to a maximum of 0.99 $\mu\text{g}/\text{kg}/\text{min}$. There was a significant improvement in oxygenation after commencement of milrinone, particularly in the first 24 h of infusion. Tachycardia improved and there was no hypotension. The same authors performed pharmacokinetic studies in 11 late preterm and term infants with PPHN resistant to iNO with a loading dose of 50 $\mu\text{g}/\text{kg}$ over 60 min followed by an infusion of 0.33 to 0.99 $\mu\text{g}/\text{kg}/\text{min}$ and demonstrated an improvement in oxygenation (figure 4) and RV / LV output and a reduction in pulmonary arterial pressure by echocardiography without any IVH (McNamara, Shivananda et al. 2012).

Recently, James et al have described 17 term infants with PPHN resistant to iNO and treated with milrinone infusion (James, Corcoran et al. 2015). An echocardiogram was obtained one hour (median) prior to milrinone infusion. Milrinone infusion increased left ventricular output, right ventricular output, right ventricle strain and strain rate. These echocardiographic changes were associated with a reduction in iNO dose and oxygen requirement over the subsequent 72 hours (James, Corcoran et al. 2015). There was a significant decrease in OI at 24 h post milrinone infusion and this effect persisted at 72 h [OI at baseline – 12 (6-21); 24 h – 5 (2-10) and 72 h – 3 (1-7)]. There was a reduction in systolic, diastolic and mean systemic blood pressures at 6 h after infusion with an increase in use of vasopressor medications. However, blood pressure began to increase after 12 h of milrinone administration with a peak at 72 h.

[figure not shown]

Figure 4. Change in oxygenation index (OI) in patients with iNO resistant PPHN (does not include patients with CDH) treated with IV milrinone. * $p < 0.05$ compared to post iNO OI (McNamara, Shivananda et al. 2012).

Pharmacokinetics of milrinone in late-preterm/term neonates: The half-life, total body clearance, volume of distribution and steady state concentration of milrinone in neonates with PPHN are shown in table 4. Similar values were obtained from 48 neonatal, post-op cardiac patients in the PRIMACORP study (table 4) which also showed that the clearance in neonates is only 25% of that in children (Bailey, Miller et al. 1999). With a constant-rate infusion, neonates take a much longer time to achieve steady-state concentration. Without a loading dose, neonates reached 50% of steady-state concentration by 2h (compared to 45min in older children). However, for the same infusion rate, the steady-state concentration will be higher in neonates than older patients. These findings underscore the necessity of a loading dose for rapid achievement of a therapeutic blood concentration in neonates, but lower infusion rate to avoid higher levels secondary to poor clearance (Bailey, Miller et al. 1999). Milrinone pharmacokinetics have also been evaluated in preterm infants (Paradisis, Jiang et al. 2007, Paradisis, Evans et al. 2009), infants following cardiac surgery (Lindsay, Barton et al. 1998, Hoffman, Wernovsky et al. 2003) and more recently in neonates with iNO resistant PPHN (McNamara, Shivananda et al. 2012) (table 4). It appears to be a safe and effective medication and has been used in 209 CDH patients without associated heart defects within the CDH

registry (Menon, Tani et al. 2012). Seventeen percent of patients with CDH in the Neonatal Research Network (NRN) are treated with milrinone.

Table 4. Pharmacokinetic data on milrinone in adults, children, term and preterm neonates

Study	Adult (Young and Ward 1988)	Child (Bailey, Hoffman et al. 2004)	Neonate (post-op CHD) (Bailey, Miller et al. 1999)	Neonate (PPHN) (McNamara, Shivananda et al. 2012)	Preterm neonate (Paradisis, Jiang et al. 2007)
Gestational age/age	Healthy adult volunteers	Pediatric patients	Neonates	39.2 ± 1.3 weeks 14h (10-30h)	26 weeks (23-28)
Weight (kg)		$5.9 \pm 4^*$		3.481 ± 0.603	0.85 (0.52-1.26)
Half-life (h)	0.8 ± 0.22	3.7		4.1 ± 1.1	10.3
Total body clearance (mL/kg/min)	6.1 ± 1.3	2.5 to 10.6 (increases with age)	1.64 ± 0.37	1.83 ± 0.17	0.64
Volume of distribution (L/kg)	0.32 ± 0.08	0.7 – 0.9	0.523 ± 0.028	0.56 ± 0.19	0.576
Steady-state concentration (ng/mL)				290.9 ± 77.7	195 (78-257) at 21h after infusion

OI at admission (n=225)	12 \pm 10 (n=123)	33 \pm 16 (n=102)	33 \pm 18 (n=73)
OI at 6 h after admission (n=127)	9 \pm 8 (n=81)	29 \pm 20 (n=46)	26 \pm 23 (n=27)
Patients with OI \geq 10, 6 h after admission (n=57)	20 \pm 8 (n=21)	35 \pm 19 (n=36)	35 \pm 22 (n=18)

* Data courtesy [name], MD – Medical College of Wisconsin; † data courtesy [name], MD – University of Iowa and ¶[name], University at Buffalo. Please note that the number of patients with arterial blood gas data available at each time point is variable as this table does not represent a single cohort.

Based on table 6, among patients with an OI ≥ 10 at 6 hours after admission, the need for ECMO and/or risk of death before discharge is $36/57 = 63\%$ and represents moderate to severe PPHN.

Use of $(\text{PaO}_2 / \text{FiO}_2) - \text{PaCO}_2$ index for stratifying severity of PPHN and lung hypoplasia in patients with CDH: The two main determinants of outcome in CDH are lung hypoplasia and PPHN. Arterial CO_2 is an important predictor of outcome in infants with pulmonary hypoplasia due to CDH (Salas, Bhat et al. 2014). Oxygenation index is also a good predictor of PPHN (Ruttenstock, Wright et al. 2015) but does not take PaCO_2 levels into account. An index that includes both oxygenation and ventilation parameters (such as $(\text{PaO}_2 / \text{FiO}_2) - \text{PaCO}_2$ index) may be a better indicator of severity of PPHN and lung hypoplasia. A cut-off value of zero for this index distributes patients into moderate and high risk of ECMO/death (table 7).

Table 7. Preliminary data: Outcomes – survival without ECMO, ECMO/death among infants with CDH with an OI of ≥ 10 6 hours after admission and stratified into severe and moderate hypoxemic respiratory failure (HRF) based on the $(\text{P/F ratio} - \text{PaCO}_2)$ index

Index @ 6h after admission & OI ≥ 10	Survived without ECMO (n=21)	ECMO and/or Died (n=37)	Died (n=18)
Severe HRF ($\text{P/F ratio} - \text{PaCO}_2$) index ≤ 0 (n=21)	3 (14%)	18 (86%)	8 (38%)
Moderate HRF ($\text{P/F ratio} - \text{PaCO}_2$) index > 0 (n=37)	18 (49%)	19 (51%)	10 (27%)

Milrinone lactate injection is currently indicated for the short-term (~48h) intravenous use in adults with decompensated cardiac failure. Being an “inodilator” and lusitrope, milrinone is likely to improve cardiac function and promote pulmonary vasodilation and be effective in managing PPHN associated with CDH.

This investigation is not intended to support a new indication for use or any significant change in labeling for milrinone. This study does not involve change in route of administration. **Only FDA approved milrinone products will be used in this study. FDA has exempted this study from requiring an IND.**

2.4. JUSTIFICATION FOR THE STUDY

Significance:

Approximately 1600 newborn infants with CDH are born in the US every year (<http://www.cherubs-cdh.org/>) and CDH is an orphan disease that is excluded from many trials involving PPHN. The overall survival based on the CDH registry is 71% (75% for isolated CDH) (<http://utsurg.uth.tmc.edu/pedisurgery/cdhsg/CDHSG.pdf>) and has not significantly improved in the last 10-15 years. The main causes of mortality are pulmonary hypoplasia and therapy-resistant pulmonary hypertension (figure 5). Survivors with CDH have long-term problems

[figure not shown]

Figure 5. Pathophysiology of hemodynamic abnormalities in congenital diaphragmatic hernia. During fetal life, reduced pulmonary venous return contributes to left sided cardiac hypoplasia. In the immediate postnatal period, a short period of better oxygenation is referred to as "honeymoon" period. Subsequently, a period of left ventricular dysfunction results in pulmonary venous hypertension. Progressive volutrauma and oxygen toxicity leads to chronic lung disease and contributes to pulmonary hypertension. Maintenance of ductal patency with intravenous PGE1 and enhanced left ventricular function with milrinone may improve oxygenation in CDH.

including pulmonary hypertension and chronic lung disease. In spite of high mortality, to date, only one randomized controlled study has been published evaluating the postnatal management of CDH. This study involving iNO

was conducted through the Neonatal Research Network and the Canadian Institute of Health Research over 15 years ago. In the past decade, significant changes in mechanical ventilation, 'gentle' approach to ventilation of newborn infants, since the NINOS-CDH study was completed, recognition of oxygen toxicity, tolerance to lower SpO₂ and higher PaCO₂ (permissive hypercapnia) and delayed surgical repair have changed the management of CDH.

Seventeen percent of patients with CDH in the NRN currently receive milrinone (same as sildenafil) (table 9, page 33). Based on case reports, compelling low-level evidence exists that

milrinone may be beneficial in PPHN and possibly CDH. There is a potential for confounding and co-intervention bias secondary to the lack of a control group in these case series (Giaccone and Kirpalani 2012). Even in a small pilot study, randomization can strengthen results and make them more interpretable (Giaccone and Kirpalani 2012).

Investigators: Congenital diaphragmatic hernia is a relatively rare condition and most patients are often referred to tertiary care centers. Approximately 10% of all cases in the US are cared for within the NRN. Many NRN investigators have experience in conducting trials on postnatal management of CDH (1997). The NRN is the ideal venue for conducting this pilot trial in the US. A successful pilot within the NRN may provide data for a multicenter definitive trial. With the change in the composition of NRN in 2016, the number of CDH patients has increased to approximately 227 / year.

Innovation: We speculate that poor response to conventional therapy in CDH is related to left ventricular dysfunction in the immediate postnatal period followed by ventilation induced oxygen toxicity and volutrauma (figure 5). (Gien and Kinsella 2016, Snoek, Reiss et al. 2016) Improving cardiac dysfunction with milrinone in combination with “gentle” ventilation may potentially improve oxygenation and reduce the risk of chronic lung disease and the need for ECMO. To our knowledge, this is the first randomized trial using an inodilator in CDH.

Approach: A prenatal consult by maternal-fetal medicine, surgery and/or neonatology is a common practice in many centers for mothers diagnosed with fetal CDH. Explaining the study to the parents and consenting during the antenatal period will allow us to enroll adequate number of patients. The intervention proposed in this protocol is intravenous infusion of milrinone, a medication that is commonly used in many NICUs. Based on the survey of NRN centers, 17% of babies with CDH already receive this medication (table 9). It is not clear if this medication is used early in the course of the disease or after documenting a poor response to iNO or secondary to the presence of ventricular dysfunction.

A potential problem with this protocol is slow recruitment. Based on the number of patients with CDH in the NRN, we anticipate that enrollment will be completed over a period of 24 to 36 months. However, if enrollment is slow over the first 6 months, it will be crucial to increase consenting during the antenatal period and to enhance involvement of pediatric surgeons at these centers.

Infants from all races and ethnicities and both genders will be included in this study. A Spanish consent form will be required by all sites with > 5% of subjects speaking Spanish only.

Environment: The Neonatal Research Network is ideally suited to conduct this pilot trial for the following reasons:

- (i) Vast experience with neonatal clinical trials
- (ii) Availability of an adequate number of patients to conduct this pilot trial
- (iii) Recent experience and training and lessons learnt from trials involving management of PPHN
- (iv) Many investigators in the NRN have experience in one of the two postnatal randomized controlled trials published in CDH population (NINOS 1997).
- (v) Excellent collaboration between neonatologists and pediatric surgeons in previous and ongoing trials (e.g., NEST – Laparotomy vs. drainage in necrotizing enterocolitis NCT01029353).

SECTION 3. STUDY DESIGN

3.1. PRIMARY OUTCOME

The primary outcome is the oxygenation response, as determined by change in OI (or OSI if no arterial blood gas is available) at 24h after initiation of study drug. In patients that require ECMO or die prior to completion of 24h from the initiation of the study drug, the last OI (or OSI, if no arterial blood gas is available) prior to initiation of ECMO or death will be used for analysis. A difference in OI of 4 points in mean change from baseline OI at 24 h between experimental and control groups will be considered significant (OI increased by 4 ± 14.8 in the control group and decreased by 2.7 ± 23.4 following iNO in the CDH NINOS study (1997). In the Patel study, following milrinone infusion, OI decreased by 2.7 ± 1.7 from baseline by 12-24 h and 5.5 ± 3.2 by 48-72 h; the mean change in OI of both these time points is a decrease by 4.1 ± 1.5 (Patel 2012)). This outcome will be used for sample size calculation. Although a decrease in OI by 4 points may not be clinically significant, this number is based on the only published case series showing the use of milrinone in CDH. In patients without an arterial line (or if the line is lost), oxygen saturation index (OSI) will be calculated using a preductal oximeter. (Rawat, Chandrasekharan et al. 2015)

Oxygenation index (OI) = Mean airway pressure (cm H₂O) x FIO₂ x 100 ÷ PaO₂ (mm Hg)

Oxygen saturation index (OSI) = Mean airway pressure (cm H₂O) x FIO₂ x 100 ÷ SpO₂ (%)

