In addition, the following markers of disease severity will be recorded if available in the medical chart (but not used for stratification):

(a) Prenatal

- a. observed to expected lung to head ratio – O/E LHR, by antenatal ultrasound
- b. position of the liver,
- c. observed to expected fetal total lung volume (O/E FTLV) assessment by fetal MRI (Ruano, Lazar et al. 2014) (Kastenholz, Weis et al. 2016),

(b) Postnatal

- a. oxygenation index (OI), = $\text{Mean airway pressure} \times \text{FiO}_2 \times 100 \div \text{PaO}_2$
- b. oxygen saturation index (OSI) = $\text{Mean airway pressure} \times \text{FiO}_2 \times 100 \div \text{preductal SpO}_2$, (Rawat, Chandrasekharan et al. 2015)
- c. evidence of pulmonary hypertension as determined by echocardiogram:
 - i. velocity of the tricuspid regurgitation jet – if present,
 - ii. the position of the inter-ventricular septum and

- iii. direction of shunt at the patent foramen ovale – PFO and patent ductus arteriosus – PDA level

(c) Intraoperative defect size (Congenital Diaphragmatic Hernia Study, Lally et al. 2007).

Exclusion Criteria:

Infants are ineligible if they meet any of the following criteria:

- known hypertrophic cardiomyopathy
 - Note 1: infants of diabetic mothers with asymmetric septal hypertrophy can be included as long as there is no evidence of obstruction to left ventricular outflow tract on echocardiogram,
 - Note 2: infants with other acyanotic congenital heart disease (CHD) and CDH may be included in the study and will be a predetermined subgroup for analysis)
- cyanotic CHD – transposition of great arteries (TGA), total anomalous pulmonary venous return (TAPVR), partial anomalous pulmonary venous return (PAPVR), truncus arteriosus (TA), tetralogy of Fallot (TOF), single ventricle physiology – hypoplastic left heart syndrome (HLHS), tricuspid atresia, critical pulmonic stenosis or atresia etc.,

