4.2.3. Randomization Procedures

The following information must be checked and/or confirmed prior to randomization. (a) chest X-ray to confirm the presence of unilateral CDH, (b) complete blood count – CBC to check platelet count and (c) a blood gas – arterial, venous or capillary to document a $\text{PCO}_2 \leq 80 \text{ mm Hg}$. These labs are routinely obtained to evaluate babies with suspected CDH in most institutions. Data from a baseline echocardiogram prior to initiation of study drug (if obtained for clinical purposes) is recorded but is not necessary for randomization (see 4.1.2 (5) above).

- (i) The diagnosis of CDH and the side of the defect must be confirmed with a chest X-ray.
- (ii) Adequate platelet count ($\geq 80,000/\text{mm}^3$) on the most recent CBC (after a platelet transfusion if necessary).
- (iii) Optional - An indwelling arterial line is placed (if not available oxygen saturation index or OSI is collected).
- (iv) Concurrent, ongoing therapy with a parenteral (IV/SQ) pulmonary vasodilator (milrinone, epoprostenol, treprostинil or sildenafil) is a contraindication to the study.
- (v) An arterial blood gas (preductal or postductal) with an oxygenation index of ≥ 10 (or OSI ≥ 5 in the absence of an arterial blood gas) and an arterial, venous or capillary blood gas with $\text{PCO}_2 \leq 80 \text{ mmHg}$ on the most recent blood gas (or pulse oximeter recording) should be recorded within 12 hours prior to randomization. An acute reversible mechanical factor such as endotracheal tube obstruction as a cause of elevated OI should be ruled out prior to randomization. If both preductal and postductal gases are available (this is rare), a preference is given to preductal – right radial or ulnar arterial draws, for calculation of OI. (Gien and Kinsella 2016) The same site (preductal or postductal) must be used at various time points for consistent comparison.
- (vi) Infants with CDH are eligible for enrollment if there are no exclusions and the most recent blood gas drawn within 12 hours prior to randomization has an OI ≥ 10 .
 - a. In patients without arterial access and/or an arterial blood gas, oxygen saturation index (OSI) can be calculated and if ≥ 5 , randomization can be performed.

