(vii) Once the infant meets these eligibility criteria and is randomized, the study drug infusion should start within 5 hours of randomization (if not, a protocol deviation form should be filled out). Once the infant is randomized, study drug is initiated even if a subsequent blood gas obtained for clinical purposes has an OI < 10 (or OSI is < 5 if there is no arterial blood gas).

Eligible infants will be randomized to either milrinone arm or placebo arm using a phone or web system in a 1:1 ratio.

4.2.4. Stratification:

Patients will be stratified based on the severity of HRF using the prediction formula (PaO₂/FiO₂ ratio – PaCO₂ value) at the time of randomization. Patients with prediction value ≥ 0 will be considered as “moderate” and infants with a value of < 0 as “severe” HRF. If arterial line is not present prior to randomization, preductal OSI value of 5 to 10 (moderate) and > 10 (severe) will be used to determine severity of respiratory failure.

In addition, side of the defect, center, prenatal (observed to expected lung to head ratio – LHR, position of the liver, lung volume assessment by MRI) (Ruano, Lazar et al. 2014), postnatal (OI (Ruttenstock, Wright et al. 2015), oxygen saturation index = mean airway pressure x FiO₂ x 100 \div preductal SpO₂) (Rawat, Chandrasekharan et al. 2015) (Park, Lee et al. 2013), evidence of pulmonary hypertension (velocity of the tricuspid regurgitation jet – if present, the position of the inter-ventricular septum and direction of shunt at the patent foramen ovale – PFO and patent ductus arteriosus – PDA level) and intraoperative (defect size) (Congenital Diaphragmatic Hernia Study, Lally et al. 2007) markers of disease severity will be recorded (but not used for stratification).

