5.1 SAMPLE SIZE AND POWER ESTIMATES

Sample Size: In the case series describing the effect of milrinone among neonates with CDH, baseline OI (mean \pm SD) was 10.6 ± 5.6 , and improved to 7.9 ± 6.2 and 5.1 ± 2.6 at 12-24 h and at 48-72 h, respectively (Patel 2012). Assuming that children receiving placebo will have no additional change in OI (mean change in OI = 0 at 24 hours), that children receiving milrinone will improve to a mean OI of 6.0 (a mean change in OI of 4.6) at 24 hours, and that the standard deviation of the change from baseline OI at 24 hours in each group is 6.2, 33 subjects in the control group and 33 subjects in the milrinone group would have 84% power to detect this difference with a two-sided alpha of 0.05 (note that 6.2 is a conservative standard deviation estimate, as data from the Patel et al study indicate that the standard deviation for change from baseline in OI at 24 hours may be as low as 1.5). Phrased differently, if both the control and treatment OI's were to change, for any given difference in OI, the sample size would be sufficient to detect an effect size of 0.7 with a power of 84%. The sample size will be sufficient to provide estimates of adverse event rates in the treatment group. The following table provides the 95% confidence intervals for observed adverse event rates varying from 6% to 49% for a sample size of 33 subjects.

Table 8. Confidence Intervals for Observed adverse event rates.

Point estimate	0.06	0.09	0.21	0.30	0.39	0.49
95% CI	(0.007, 0.2)	(0.02, 0.24)	(0.09, 0.39)	(0.16, 0.49)	(0.23, 0.59)	(0.31, 0.66)

Within the NRN centers, approximately 36% of neonates with CDH who are \geq 36 weeks PMA require ECMO. In a selective population (isolated CDH with OI \geq 10), we estimate that the risk of ECMO or death prior to discharge (or by day 120) will be approximately 40%. A sample size of 33 in the placebo arm would provide a 95% confidence interval for this estimate of (26%, 58%). The precision of estimates for outcome rates in the treatment group can be seen in table 8.

Limitations:

- (a) This study is not powered to compare rates of the outcome of death or ECMO between groups. To detect a reduction of 10% (from 40% incidence of death/ECMO in control arm to 30% incidence in the milrinone arm), with a 1:1 ratio of treatment and control subjects, a power of 0.8 and an alpha value of 0.05, we would require 376 subjects in each arm.

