5.4 STATISTICAL ANALYSIS PLAN

Baseline data will be collected prior to randomization including gestational age, side of the diaphragmatic hernia, birth weight, mode of delivery and arterial blood gas parameters (oxygenation index-OI) and/or pulse oximetry data (oxygen saturation index-OSI). Data from a baseline clinical echocardiogram is recorded (if performed prior to study drug initiation or within 2h of initiation of study drug). During the infusion of study drug, arterial blood gas parameters and hemodynamic data (blood pressure, heart rate and echocardiography results) will be recorded. After completing the study infusion, surgical details, and mortality information will be collected. Among survivors, respiratory and nutritional status at discharge and at 4, 8 and 12 months of age will be collected.

Data will be presented as mean \pm SD for normally distributed variables and as median and ranges (with percentiles) for non-normally distributed data. All analysis will be by intention-to-treat. Baseline characteristics will be compared between treatment groups using chi-square and Fisher's exact test for discrete variables and t-test and ANOVA for continuous variables. The primary outcome, difference from baseline OI at 24 h, will be compared between treatment groups using a general linear model adjusted for the stratification factor of HRF severity. Other continuous outcomes will be analyzed similarly. Models for longitudinal outcomes such as oxygenation and vasoactive inotrope scores (short-term) and nutritional and pulmonary outcomes at 12 months (long-term) will include the effect of time, the interaction between time and treatment, and random effects to account for the correlation between measures taken on the same individual over time. Categorical outcomes will be analyzed using analogous generalized linear models. Cox regression models (with adjustment for HRF severity) will be used to plot proportion of responders who survive without ECMO against survival time in hours. Analyses may adjust for clinical site if treatment assignments are severely imbalanced for some sites provided that it is computationally feasible to do so. The potential influence of baseline measures such as time of diagnosis – antenatal vs. postnatal, side of the defect, and gender on pulmonary and nutritional outcome will be explored through the use of additional models similar to those described above.

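### The primary outcome substitutes OSI for OI without a same-index rule or a stated way for OSI changes to enter a model and criterion set in OI units

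*Combined protocol and SAP*

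**What the plan says.** The summary and section 3.1 define a single primary change score: "The primary outcome is the oxygenation response, as determined by change in OI (or OSI if no arterial blood gas is available) at 24h". Section 3.1 adds: "In patients without an arterial line (or if the line is lost), oxygen saturation index (OSI) will be calculated using a preductal oximeter". For infants who need ECMO or die before 24 h, the last value of either index is used.

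The figures against which the result will be read are in OI. Section 3.1 gives the criterion as "A difference in OI of 4 points in mean change from baseline OI at 24 h between experimental and control groups". Section 5.1 assumes that "the standard deviation of the change from baseline OI at 24 hours in each group is 6.2", with a mean improvement of 4.6 on milrinone and none on placebo. Section 5.4 says: "The primary outcome, difference from baseline OI at 24 h, will be compared between treatment groups using a general linear model". It adjusts for HRF severity and is by intention-to-treat. That section lists baseline data as OI and/or OSI but does not say how an OSI change enters the model.

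The nearest consistency rule is in section 4.2.3: "The same site (preductal or postductal) must be used at various time points for consistent comparison". It concerns where blood is sampled, not which index is used. The same section makes an arterial line optional, and section 4.1.1 lets an infant enter on OSI alone.

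**The concern.** OI and OSI are different scales. The protocol itself pairs an OI of 10 with an OSI of 5 for eligibility, 7 with 3.5 for ending the infusion, and 40 with 20 for the ECMO or death floor. One OSI point therefore stands for roughly two OI points. If both kinds of change go into one model unconverted, the estimate is in mixed units, and the mix depends on how many infants happen to lack an arterial gas.

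There is a second route to trouble. Baseline is the 30 minutes before study drug (section 4.2), and no blood is drawn for research (section 4.2.5). Whether a gas exists at baseline and again at 24 h therefore depends on clinical sampling. Nothing in sections 3.1 or 5.4 rules out OI at one time and OSI at the other for the same infant. An unchanged infant who goes from OI to OSI would seem to improve; one who goes from OSI to OI would seem to worsen.

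The trial is a pilot meant to inform a larger one, so the size of the estimate matters as well as its p-value.

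**Working it through.** **Inputs.** Effect 4.6, SD of change 6.2, 33 per arm, two-sided alpha 0.05 (section 5.1); baseline OI 10.6, SD 5.6 (section 5.1); criterion 4 points (section 3.1). The documents give neither the share p of infants on OSI nor the rate of switching, so both are assumptions.

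**1. The plan's power.** SE = 6.2 × √(2/33) = 1.53. A two-sample t-test on 64 df gives 84.3%, matching the stated 84%. The sample-size arithmetic is not at fault.

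**2. The ratio of the scales.** By the formulas in section 3.1, OI/OSI = SpO2/PaO2 when both are measured together. Call this r. The paired thresholds give 10/5 = 7/3.5 = 40/20 = 2, but r varies with the infant, so 2:1 is approximate. I also use r = 1.4.

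**3. OSI at both times in a share p, pooled unconverted.** Expected estimate = 4.6 × [1 − p(1 − 1/r)]. Power is by simulation with an unadjusted t-test.

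| r | p | Expected estimate | Power |
|---|---|---|---|
| any | 0 | 4.60 | 84% |
| 2 | 25% | 4.6 × 0.875 = 4.03 | 82% |
| 2 | 50% | 4.6 × 0.75 = 3.45 | 80% |
| 1.4 | 25% | 4.6 × 0.929 = 4.27 | 84% |
| 1.4 | 50% | 4.6 × 0.857 = 3.94 | 83% |

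Power barely moves because the SD shrinks along with the effect. The expected estimate falls below 4 once p exceeds (1 − 4/4.6)/(1 − 1/r), which is 26% at r = 2 and 46% at r = 1.4.

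**4. A switch within one infant.** With no true change and baseline OI of B, going from OI to OSI scores −B(1 − 1/r). At B = 10.6 this is −5.3 for r = 2 and −3.0 for r = 1.4. The reverse switch gives the same size with a plus sign. These are artefacts in one infant, not group effects.

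**5. OI-to-OSI switching in both arms alike.** At 10% / 20% of infants, simulated power is about 81% / 78% at r = 2 and 83% / 82% at r = 1.4. This simulation draws change independently of baseline and so produces some impossible negative values at 24 h. Flooring the 24 h OI at 1 cuts the effect itself to 3.73 and power to 80% without switching, then to 75% / 70% with 10% / 20% switching at r = 2. The direction is the same.

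**6. Type I error.** With equal switching it stays at about 5%. If 10% switch in one arm and 20% in the other at r = 2, the bias is 0.10 × 10.6/2 = 0.53 points, and simulated type I error is between 6% and 7%.

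**7. Doubling OSI as a repair.** Expected estimate = 4.6 × [1 + p(2/r − 1)]. At r = 1.4 and p = 50% this is 5.59, an error of +0.99, against 3.94 (−0.66) with no conversion. The two errors are equal in size when 1 − 1/r = 2/r − 1, that is at r = 1.5. Below that, doubling is further from the truth.

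**The case against.** Pooling in one model is an inference. Section 5.4 names only OI and is silent on OSI infants. That is so, but the alternative, analysing OI alone, would drop infants from an intention-to-treat analysis and is not stated either.

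A reader might infer that the result cannot be read against 4 points at all. That goes too far. With 20% on OSI at 2:1 the expected estimate is 4.6 × 0.9 = 4.14, still above 4. Nor is 4 points a pass mark on the estimate in section 5.4, which specifies a model comparison and no 4-point rule. Section 3.1 uses the figure for sample size and concedes that it may not be clinically significant. With SD 6.2, p < 0.05 needs an observed difference of only about 2.00 × 1.53 = 3.05.

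A reader might also infer that switching will happen. The documents permit it but do not show it. Losing a line does not force OSI, since section 3.2 also recognises arterial sticks. An umbilical sample is postductal and OSI is preductal, so that switch arguably breaches the same-site rule in section 4.2.3. A switch from a right radial sample to OSI is not covered by that rule.

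Finally, the manual of procedures, to which the protocol defers other definitions, is not among these documents and may hold a rule. Sections 3.1 and 5.4 do not point to it for this outcome.

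**Conclusion.** The point stands as a gap in the definition and analysis of the primary outcome that should be closed. Followed literally, the substitution rule mixes two scales and leaves the index free to change within an infant. At the assumed OSI shares of 25% and 50%, a true 4.6 reads about 4.0 and 3.45 at a ratio of 2, or 4.3 and 3.9 at 1.4. If few infants are on OSI and none switch, the shift is small.

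It would be tempting to conclude that the trial is underpowered or its test invalid for this reason. The figures do not support that. With one index per infant the loss of power is at most about 4 percentage points over the range examined. Type I error moves from 5% only if switching differs by arm, which nothing in the documents indicates. The harm is mainly to interpretation on the OI scale.

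**What to change.** Amend sections 3.1 and 5.4 as follows.

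1. Form each infant's change from the same index at both times: OI if a gas exists at both, otherwise OSI at both. To make this always possible, record preductal SpO2 with mean airway pressure and FiO2 for every infant, including those with an arterial line, at baseline, at 24 h and at the last value before ECMO or death. Inspired oxygen and ventilator data are already planned six-hourly (section 3.2 (v)). For OI and OSI as severity markers, however, the summary says only that "the following markers of disease severity will be recorded if available in the medical chart", and section 4.2.4 names no time point.
2. Do not average unconverted OI and OSI changes. Prespecify how OSI-only infants enter the model. Report an OSI-for-all analysis, which needs no conversion and keeps every infant, and an analysis limited to infants with OI at both times. Read the 4-point criterion only against results on the OI scale.
3. Report the number analysed on each index, by arm.
4. Apply the same rule to the 48 h and 72 h outcomes and to the analysis with the 40/20 floor.

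Doubling OSI should be at most a labelled sensitivity analysis, because it overstates the effect whenever SpO2/PaO2 is below 2. If the manual of procedures already holds a rule, state it in sections 3.1 and 5.4.

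The cost is wording, one oximeter value per time point and a little more analysis.
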